### Attention Control (AC) Group

Women who are randomized into the AC will participate in an 10-week education program delivered by group videoconference platform supported by UTN. The education program is manualized and designed to enhance participant knowledge related to pregnancy, childbirth, newborn care, and feeding, or parenting young babies. All participants in the AC group will receive a mailed hard copy and/or emailed electronic packet (participant’s choice) that includes topical education, which includes information about perinatal depression and mood disorders (e.g., anxiety and obsessive-compulsive disorder, postpartum psychosis), interpretation of EPDS scores, common therapies for PD, local resources for obtaining therapies, and encouragement to discuss their EPDS scores with their prenatal care provider. This approach provides a control group that reduces bias as much as possible, and most closely reflects an optimal care level that includes screening and patient education for all pregnant and postpartum women.

### Data Collection

Data collected for this study will come from the following sources: Clinical universal screening records (the EPDS in the electronic health record [EHR]), participant-completed study questionnaires, audio-recorded VCI sessions, and participant focus groups. EPDS is a validated survey.

#### Clinical Screening Records

Screening that is completed in the clinical setting as part of their routine clinical care is immediately communicated to and addressed by clinical providers at the time of the prenatal or postpartum visit. EPDS and GAD-7 measurements completed periodically and

electronically by enrolled participants as part of the study (not as part of their routine clinical care) are evaluated and addressed by study personnel within 24-48 hours of completion. Participants are contacted directly by study personnel for scores >20 on the EPDS, or if the participant indicates thoughts of harm to self. Furthermore, the EPDS and GAD-7 are electronically scored, interpreted, and communicated to the participant immediately. At that same time, participants also receive electronic resources, including crisis and suicide prevention hot line phone numbers, website links, and study personnel contact information.

#### Participant-Completed Questionnaires

Questionnaires will be completed by participants via a secure, Web-based data management system (REDCap). Women in all study groups will receive an emailed link to the questionnaire. Study questionnaires are to be completed at six time points: T1 = enrollment; T2 = after group session 9; T3 = 2 months post session 9 T4 = 4 months post session 9; T5=6 months post session 9; T6= 8 months post session 9. In addition to participant demographics, questionnaires will include the EPDS as a measure of the primary outcome of interest: depressive symptoms, as well as the GAD-7 as a measure of comorbid anxiety (GAD-7 is a validated survey). To document the standard of care that all participants receive during study participation, the questionnaire at all six-time points also asks participants to report whether they (1) received a diagnosis of depression, anxiety, or other mental health condition; (2) were prescribed or initiated any medication for depression or anxiety; (3) were referred to and/or engaged in mental health services; and/or (4) have engaged in any type of nonpharmacological therapies for depression/anxiety during the study. If a participant does not have an email address, study staff will assist her to establish and access a free email address. All participants will receive instruction on how to access and complete the study questionnaires. The entire questionnaire takes approximately 15 minutes to complete. Participants receive \$20 for each questionnaire completed.

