
## Purpose and Objectives

---

The study will evaluate the effectiveness of a videoconference intervention (VCI) to reduce perinatal depression symptoms (PDS) and anxiety (a highly co-morbid condition) by conducting a randomized controlled trial among women experiencing mild to moderate PDS, as measured by the Edinburgh Postnatal Depression Scale (EPDS). Furthermore, we propose to evaluate differences in response to the VCI between subgroups of childbearing women; Hispanic and North European Descent populations, and rural and urban-dwelling.

Specific aims of the study include:

Aim 1: Evaluate the effectiveness of a VCI to reduce PDS and anxiety, as measured by EPDS and Generalized Anxiety Disorder-7 Item (GAD-7) scores across pregnancy and the postpartum. Methods: Pregnant women of all gestational age up to 6 months postpartum (n = 240) who screen positive for mild to moderate PDS (EPDS scores 9–20) will be randomly assigned to VCI or AC for eight weeks. Both groups will continue with standard care as directed by their primary/prenatal care providers. The EPDS and GAD-7 will be administered at three time points during pregnancy and at 2, 4, and 6 months postpartum. Hypothesis: Women participating in the VCI will have significantly lower post intervention EPDS and GAD-7 scores across pregnancy and postpartum than women in the AC group.

Secondary Aim 1: Explore differences in the effectiveness of the VCI to reduce PDS and anxiety across women who enroll at different stages of their pregnancy or postpartum periods.

Aim 2: Evaluate the interaction of the VCI with specific subgroups: ethnicity (Hispanic, North European descent), geographic location (rural, urban), and the outcome of PDS as measured by EPDS and GAD-7 scores across pregnancy and postpartum. We will oversample in Hispanic and rural populations to ensure sufficient representation from diverse groups. Hypothesis: Women will demonstrate differences in EPDS and GAD-7 scores across pregnancy and postpartum, dependent on their study group membership.

Secondary Aim 2: Explore an additional subgroup analysis, namely between those who are and who are not taking medication at the time of screening.

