#### VCI Participants

A study team member will contact the participant by telephone and/or email to determine which group start date works best for her and to schedule a time for technology testing and instruction.

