#### All Participants: Technology Literacy

Prior to the start date of the first VCI or AC session, each participant will meet with study staff for the purpose of (1) assessing the participant's technology literacy, (2) testing the participant's Internet connection and chosen electronic device, and (3) providing instruction and demonstration for connecting to the videoconference platform (Acano). More than one meeting may be required and will include meeting via Acano and troubleshooting directly

with the participant. After this is completed to the satisfaction of the participant and study staff, the next step will be to schedule the participant to meet with the VCI group facilitator via Acano.

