Participant-Completed Questionnaires. Questionnaires will be completed by participants via a secure, Web-based data management system (REDCap). Women in all study groups will receive an emailed link to the questionnaire. Study questionnaires are to be completed at six time points: T1 = enrollment; T2 = post intervention ; T3 = 2 months post intervention GA; T4 = 4 months post intervention; T5= 6 months post intervention; T6= 8 months post intervention. In addition to participant demographics, questionnaires will include the EPDS as a measure of the primary outcome of interest: depressive symptoms, as well as the GAD-7 as a measure of comorbid anxiety. To document the standard of care that all participants receive during study participation, the questionnaire at all six-time points also asks participants to report whether they (1) received a diagnosis of depression, anxiety, or other mental health condition; (2) were prescribed or initiated any medication for depression or anxiety; (3) were referred to and/or engaged in mental health services; and/or (4) have engaged in any type of nonpharmacological therapies for depression/anxiety during the study. If a participant does not have an email address, study staff will assist her to establish and access a free email address. All participants will receive instruction on how to access and complete the study questionnaires. The entire questionnaire takes approximately 15 minutes to complete. Participants receive \$20 for each questionnaire completed.

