### **Data Analysis:**

We will compare demographics, partum group, and medications between groups ( $\chi^2$ ) to document the results of our randomization process. We will further document and test for differences in frequency and means in groups related to additional study-related variables. Examples include dose of participation and birth complications or pre-term deliveries. We will explore the addition of these variables in our analytical models.

We will utilize multilevel generalized mixed modeling (via SPSS and R) under an intent-to-treat (ITT) approach to compare the outcome measures of EPDS and GAD-7 between Group 1 (VCI) and Group 2 (AC) at up to six time points. To assess whether we will need to nest participants within clusters (Level 3, group-level) given that the intervention/control are administered in groups, we will conduct an analysis that adds an additional level (nesting participants within clusters) to our proposed model and calculate the model's ICC. As an exploratory analysis, for both aims, we will add the fixed effect of baby's sex to final models and report results.

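### Follow-up is dated from session 9, so a randomised woman never placed in a group, or disqualified before one starts, has no T2–T6 dates and can drop out of the intent-to-treat comparison

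*Combined protocol and SAP*

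**What the plan says.** Under Data Collection, Participant-Completed Questionnaires, the six time points begin "T1 = enrollment; T2 = after group session 9; T3 = 2 months post session 9", and T4 to T6 follow at 4, 6 and 8 months after session 9. The section Procedures performed for research purposes only gives a parallel list: "T2 = post intervention ; T3 = 2 months post intervention GA". Purpose and Objectives, Aim 1, has a third schedule, not tied to any session: "The EPDS and GAD-7 will be administered at three time points during pregnancy and at 2, 4, and 6 months postpartum".

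Stratified Randomization Into Study Groups places randomisation directly after consent. Three steps then stand between randomisation and a first session:

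- For VCI women, staff make contact to "determine which group start date works best for her" (VCI Participants).
- All women have a technology check, possibly over several meetings. "After this is completed to the satisfaction of the participant and study staff", the facilitator meeting is scheduled (All Participants: Technology Literacy).
- The facilitator meets each woman in either arm and may identify concerns that disqualify her from the study. The examples given include severe depression and suicidal ideation (Individual Participant Acano Meeting with VCI or AC Group Facilitator).

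Both Data Analysis sections specify a mixed model; the one under Statistical Methods says it is run "under an intent-to-treat (ITT) approach". Neither defines the intent-to-treat set or says how missing outcomes are handled.

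**The concern.** Every follow-up date in the two questionnaire schedules hangs on an event that comes after randomisation and that some randomised women will not have. For a woman never placed in a group there is no session 9 and no end of intervention, so nothing triggers T2–T6. Followed literally, she contributes at most T1, which says almost nothing about the Intervention × Time effect for which the sample is powered.

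The losses need not be random. The facilitator meeting removes women partly for severe symptoms, which is the primary outcome domain. Failure to start may also differ between a therapy arm and an education arm. If so, the analysed follow-up data describe women who reached a group, and the balance created by randomisation is no longer guaranteed among them.

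**Working it through.** **1. Who has due dates?**

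| Randomised woman | Session-9 date? |
|---|---|
| Placed in a group and attends | Yes |
| Placed in a group, stops or never attends | Yes, if session 9 means the cohort's calendar date |
| Never placed (scheduling or technology check not completed) | None stated |
| Disqualified at the facilitator meeting before a group starts | None stated |

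The gap is certain only for the last two rows.

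**2. Power statement.** Inputs from Data Analysis (Procedures): N = 192, m = 6 measures, correlation 0.3, f = 0.1, two arms. For the within–between interaction:

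- λ = f²·N·m/(1 − ρ) = 0.01 × 192 × 6/0.7 = 16.46
- df = 5 and (192 − 2) × 5 = 950
- Power at alpha 0.05 = 89.8%, which matches the stated figure of more than 90% to within rounding. (The text prints alpha as 0.5, which would give 99.6%; I take this as a misprint.)

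Enrolment is 240, and 240 × 0.80 = 192. If 10% of 240 had no follow-up, 216 would remain (power 93.3%); at 15%, 204 (91.7%); at 20%, 192 (89.8%). Losses on this scale fit within the existing margin if there is no other attrition. If they came on top of the planned 192, a 10% loss would give 85.9%.

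**3. Bias.** The documents give neither a never-start rate nor a prognostic gap, so these are assumptions:

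- p_V = 5% to 15% (VCI) and p_A = 5% (AC) never start.
- Without treatment, non-starters score d = 3 EPDS points higher than starters at follow-up, and the gap is not present at T1.
- VCI lowers EPDS by 1 point in women who start and by nothing in those who do not. One point is roughly the plan's target, although the plan states it per time point.

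Randomisation makes the overall untreated mean M equal in the two arms, so the untreated mean of starters is M − p·d in each. Then:

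- Benefit seen in starters only = 1 + (p_V − p_A)·d
- Benefit in all randomised = (1 − p_V) × 1
- Gap = (p_V − p_A)·d + p_V

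| p_V | p_A | Starters only | All randomised | Gap |
|---|---|---|---|---|
| 5% | 5% | 1.00 | 0.95 | 0.05 |
| 15% | 5% | 1.30 | 0.85 | 0.45 |
| 5% | 15% | 0.70 | 0.95 | −0.25 |

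The third row swaps the arms: the selection part changes sign and the starters-only result understates the benefit.

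If the 3-point gap is already present at T1, starters differ by the same (p_V − p_A)·d at T1. It then cancels from a starters-only comparison of change from T1, leaving only the dilution part, 0.05 to 0.15 points for p_V of 5% to 15%.

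**4. Effect on false positives.** With no true effect, only the selection part matters. At one time point with 96 per arm and SD 5, SE = 5 × √(2/96) = 0.722. A shift of (0.15 − 0.05) × 3 = 0.30 points is 0.30/0.722 = 0.42 SE, and the two-sided 5% test rejects about 7% of the time. A harsher assumption, a 10-percentage-point differential loss with a 5-point gap, gives a 0.5-point shift and about 11%.

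**The case against.** A reader might infer that the trial will simply compare women who started. The documents do not say that. No section excludes non-starters. The analysis is declared intent-to-treat, and the questionnaire section says "Women in all study groups will receive an emailed link to the questionnaire", with no attendance condition. Session 9 can fairly be read as the cohort's calendar date, which covers scheduled women who do not attend. A likelihood mixed model that treats T1 as an outcome would also keep T1-only women formally in the analysis. All of this stands, and it confines the gap to women who are never placed or are disqualified first. For them, being on the mailing list does not say when a link is sent, and a model holding only T1 relies on missing-at-random, which is doubtful when removal follows severe symptoms.

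Aim 1 does give a schedule independent of sessions, so it would be wrong to say that every passage ties follow-up to session 9. But that schedule conflicts with the other two, and its pregnancy time points cannot apply to women enrolled postpartum, so it is not a ready fallback.

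Nor is the wait for a group without any limit: Group VCI Sessions sets gestational limits for starting and finishing VCI. No such limit is stated for AC or for postpartum women, and those limits need to be reconciled with the eligibility criteria.

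Finally, dating outcomes from the end of the programme is a defensible choice for a treatment delivered in cohorts. Counting from randomisation instead could put T2 before or during the sessions.

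**Conclusion.** The concern holds in a limited form. As written, a randomised woman who is never placed in a group, or is disqualified before one starts, has no T2–T6 due dates, so the declared intent-to-treat comparison can lose women for reasons related to symptoms and possibly to arm. That it will become a starters-only analysis is an inference the documents do not support.

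The size is unknown because no never-start rate is given. The range of about 0.05 to 0.45 EPDS points rests wholly on the stated assumptions and on raw follow-up means, not on the Intervention × Time effect. The upper end should not be read as nearly half the target effect being at risk: it needs VCI to lose three times as many women as AC and a prognostic gap that appears only after T1. The direction of the selection part depends on which arm loses more women. Bias, not power, is the reason to act. The change should be made prospectively, because outcomes not collected cannot be recovered at analysis.

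**What to change.** In Participant-Completed Questionnaires and in the matching text under Procedures performed for research purposes only:

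1. At randomisation, assign every woman a reference date equal to the planned session-9 date of her assigned cohort, or of the next available cohort in her arm and stratum.
2. Send the T2–T6 REDCap links on dates counted from it, whether or not she attends, is placed in a group, or is disqualified from the sessions at the facilitator meeting, unless she withdraws consent. The facilitator section should say that leaving the sessions does not end questionnaire follow-up; the clinical decision itself is not touched.
3. In Data Analysis, define the intent-to-treat set as all randomised women, include all these responses in the model, and report non-starters by arm.
4. Reconcile the Aim 1 schedule in Purpose and Objectives with the two questionnaire schedules.

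The cost is protocol wording, a REDCap scheduling rule and a few more $20 questionnaire payments. For some women T2 will differ somewhat from their actual ninth session.

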#### Focus Groups

Participants will be invited to attend one focus group interview with 6-8 other participants, again using the UTN-supported videoconference platform, and within 8 weeks of completing the last group session (VCI or AC). The purpose of the focus group is to collect data directly from participants regarding satisfaction with the program, e.g. program content, videoconference platform, development of community, support, suggestions for improvement, etc. Participants receive \$20 for attending the focus group.

#### Digital Recording of Sessions and Focus Groups

To document and evaluate intervention and attention control group fidelity and standardization, and for future qualitative data analysis, we will record all focus groups, and a random selection of sessions. The Acano platform has recording capability built into the Web-based program, and is managed by UTN. The recording is unobtrusive and runs seamlessly in the background, unnoticed by facilitators or participants. Acano is a secure, HIPAA-compliant program. All participants are informed that sessions may be recorded, and this is also part of the informed consent process and consent document. The digital recordings are stored securely in a shared, password-protected file system, backed up continuously, and protected

by the UTN and U of U firewalls. Recordings are transcribed by a professional transcriptionist, de-identified, and uploaded to a secure, shared file on the U of U protected electronic environment.

## **Data Analysis**

We will use multilevel generalized mixed modeling under an intent-to-treat approach to compare the outcome measures of EPDS and GAD-7 between group 1 (VCI) and Group 2 (AC) at six-time points during pregnancy and postpartum. This is an appropriate statistical approach for the described RCT protocol. Sensitivity analysis was conducted with G-Power 3.1. We used RMANOVA with 6 total measures as a conservative power analysis for our mixed-effects model. The sample is powered for the fixed effect of Intervention X Time. For study aim 1: Using RMANOVA with alpha = 0.5, 6 total measures, 0.3 for correlation between repeated measures, and a sample size of 192 total participants gives greater than 90 percent power to detect an effect size of 0.1, which is a net decrease in EPDS and GAD-7 of roughly 1 point decrease per time point, assuming a standard deviation of 5. For study aim 2: For the stratified samples of urban/rural or Hispanic/NED, we have greater than 80 percent power to detect the same Intervention X Time effect size of 0.1.

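### T1 (enrollment) is one of the six compared time points, but no use of the T1 EPDS or GAD-7 score as a baseline is stated, so treatment contrasts may be less precise than the collected data allow

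*Combined protocol and SAP*

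**What the plan says.** The Data Analysis section under Study Procedures uses multilevel mixed modelling by intention to treat "to compare the outcome measures of EPDS and GAD-7 between group 1 (VCI) and Group 2 (AC) at six-time points". The Data Analysis text under Statistical Methods, Data Analysis and Interpretation repeats this for "between Group 1 (VCI) and Group 2 (AC) at up to six time points".

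Participant-Completed Questionnaires fixes the schedule: "T1 = enrollment; T2 = after group session 9", then two-monthly visits to T6. The version under Procedures performed for research purposes only also has T1 at enrollment and T2 after the intervention. One of the six compared measurements is therefore taken before treatment.

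The power statement counts the same six: "We used RMANOVA with 6 total measures as a conservative power analysis for our mixed-effects model". It adds: "The sample is powered for the fixed effect of Intervention X Time".

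The second analysis section names dose of participation, birth complications and preterm delivery as variables to explore in the models, and baby's sex as an exploratory fixed effect. The T1 score is not among them. The check on randomization covers demographics, partum group and medications. Randomization is stratified by ethnicity and urban or rural residence, not by symptom score.

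**The concern.** Randomized arms have the same expected T1 score. An analysis that ignores this gives up precision.

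If T1 is an ordinary response with its own mean in each arm, two common contrasts treat it poorly. A change-from-T1 contrast subtracts the whole chance difference at T1, which is too much when the correlation is below 1. A post-session contrast subtracts none of it. Adjusting for T1, or constraining the T1 means to be equal, removes the part that T1 predicts.

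What is at stake is precision and pre-specification for EPDS, GAD-7 and the Aim 2 subgroup models. The Aim 1 hypothesis concerns scores after the intervention, so nothing in it requires an arm difference at T1 to be estimated.

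**Working it through.** **Inputs.** From the Data Analysis section: SD 5, correlation ρ = 0.3 between visits, 6 measures, 192 women, effect size f = 0.1. From the enrollment goals: 240 women, 120 per arm. From the inclusion criteria: EPDS 9 to 20. Assumptions: equal correlation between all visits and, except where stated, equal SDs.

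**The plan's own figure.** For the within-between interaction, λ = f²·N·m/(1−ρ) = 0.01 × 192 × 6 / 0.7 = 16.46, with 5 and 950 degrees of freedom. Power is 89.8% at alpha 0.05, close to the stated figure of over 90%. Alpha is printed as 0.5, which gives 99.6%; I take 0.05 as intended. The inputs are therefore usable.

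**Chance imbalance at T1.** The SE of the T1 arm difference at 120 per arm is 5·√(2/120) = 0.645, a 95% range of about ±1.27 points (about ±0.9 if the T1 SD is 3.5, an assumption). The plan's effect is roughly 1 point per time point. A one-SE imbalance shifts a visit contrast by 0.3 × 0.645 = 0.19 and a change contrast by −0.7 × 0.645 = −0.45. T1 adjustment brings both to about 0.

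**Variance of the arm contrast, in units of 2·SD²/n per arm**

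- Single visit: change 2(1−ρ) = 1.40; post-only 1; adjusted 1−ρ² = 0.91.
- Mean of T2 to T6, with a = (1+4ρ)/5 = 0.44: change a+1−2ρ = 0.84; post-only a = 0.44; adjusted a−ρ² = 0.35.
- Linear arm-by-time slope, times 0 to 5: with a free T1 difference, (1−ρ)/17.5 = 0.7/17.5 = 0.040. With equal T1 means, T2 to T6 given T1 have covariance 0.7·I + 0.21·J (I the identity matrix, J all ones). The information is (55 − 0.12 × 15²)/0.7 = 40, so the variance is 1/40 = 0.025.

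| Contrast (ρ = 0.3) | Unadjusted / adjusted | SE at 120 per arm, points |
|---|---|---|
| Single visit, change | 1.40/0.91 = 1.54 | 0.764 v 0.616 |
| Single visit, post-only | 1/0.91 = 1.10 | 0.645 v 0.616 |
| Linear slope | 0.040/0.025 = 1.6 | not computed |
| Mean T2–T6, change | 0.84/0.35 = 2.4 | 0.592 v 0.382 |
| Mean T2–T6, post-only | 0.44/0.35 = 1.26 | 0.428 v 0.382 |

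**Other correlations (assumed), mean of T2 to T6**

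- ρ = 0.5: a = 0.60; change 0.60/0.35 = 1.71; post-only 0.60/0.35 = 1.71.
- ρ = 0.7: a = 0.76; change 0.36/0.27 = 1.33; post-only 0.76/0.27 = 2.81.

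The change ratio falls and the post-only ratio rises. Adjustment is the more precise in each case.

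**Entry range for EPDS.** If T1 scores are uniform on the 12 integers 9 to 20, the T1 variance is (12²−1)/12 = 11.92 and the SD is 3.45, or 0.690 of 5. The T1 variance is then 0.477 in units of SD².

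- Correlation held at 0.3: change = 0.44 + 0.477 − 2 × 0.3 × 0.690 = 0.502; ratio 0.502/0.35 = 1.43.
- Regression slope held at 0.3: post-only = 0.35 + 0.09 × 0.477 = 0.393; change = 0.393 + 0.477 − 2 × 0.3 × 0.477 = 0.584; ratios 1.67 (change) and 1.12 (post-only).

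**The case against.** The strongest reply is that the plan is silent rather than wrong. It gives no equation, parameterization or primary contrast. A reader might infer that it commits to a separate arm mean at T1, or rules out baseline adjustment. The text supports neither, and an analyst could set up the model well without departing from it. That stands, and it is why the point is worded as an omission.

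A reader might also infer that every arm-by-time contrast is a change from T1. It is not. A slope weights T1 as one visit among six, and a contrast among T2 to T6 does not use it. The plan's phrase about a decrease per time point can be read as a slope.

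It is also fair that the largest ratio depends on averaging five visits against one T1 measurement, a contrast the plan does not name. The analysis sentence reads most directly as visit by visit. There, against a post-only contrast, adjustment saves only 9% of variance.

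Finally, this is efficiency, not validity. Chance imbalance is already reflected in the standard error, and unadjusted contrasts remain unbiased. The unnamed primary contrast is the larger gap, because it decides which ratio applies.

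None of this removes the point. Every contrast worked above is more precise with T1 used as a baseline, and leaving its handling open lets the choice be made after the data are seen.

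**Conclusion.** The point holds as a recommendation. The plan does not say how the T1 score enters the model, and the treatment contrasts may be less precise than the data allow. At the plan's correlation of 0.3 and equal SDs, the excess variance runs from 10% (single-visit post-only) through 54% to 60% (single-visit change, slope) to 140% (change to the mean of T2 to T6). For EPDS, that last figure drops to about 43% to 67% under uniform entry scores.

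Three stronger conclusions are not supported:

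- **The trial needs 2.4 times as many women.** That ratio belongs to one contrast, one correlation and equal SDs. It cannot be assumed for GAD-7 either: GAD-7 has no entry limit, but women are selected on EPDS, and the plan calls anxiety highly comorbid.
- **The results would be biased.** Over-correction or non-correction of chance imbalance costs precision; it does not create bias over repeated randomizations.
- **A specific amount of power is lost.** This depends on an effect pattern the plan does not settle. If 1 point per visit accumulates over T2 to T6, the mean difference is (1+2+3+4+5)/5 = 3 points and power exceeds 99% under all three analyses of that mean at 192 women.

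The figures assume equal correlations between visits, complete data and no clustering by session group.

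**What to change.** State one of the following in both analysis sections, in the same form for EPDS, GAD-7 and the Aim 2 models:

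- Model T2 to T6 as the outcomes, with the T1 value of the same scale and its interaction with visit as covariates.
- Keep all six visits as responses and constrain the two arm means to be equal at T1. This also keeps women who have only a T1 score.

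Name the primary contrast in the same place.

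Add to the procedures that the T1 questionnaire is completed before the participant or staff know the arm. Randomization follows consent and T1 is at enrollment, but the order of the two is not stated, and both forms of the fix rely on it.

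The cost is one analysis sentence, a few degrees of freedom per outcome and, if T1 does not already come first, a change in the order of procedures. No additional data are required.

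Adjustment removes only the part of the noise that T1 predicts, so the gain should be described in those terms.

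### No contrast is named to decide Aim 1; the only effect named, Intervention X Time over six visits including enrollment, shows neither level nor direction and is the weaker test for a sustained benefit

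*Combined protocol and SAP*

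**What the plan says.** The hypothesis under Aim 1 (Purpose and Objectives) is directional and concerns level: "Women participating in the VCI will have significantly lower post intervention EPDS and GAD-7 scores across pregnancy and postpartum than women in the AC group".

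The Data Analysis section under Study Procedures plans a mixed model under intention to treat. Its power paragraph names one effect, "The sample is powered for the fixed effect of Intervention X Time", and gives the basis: "We used RMANOVA with 6 total measures as a conservative power analysis for our mixed-effects model". The inputs begin "Using RMANOVA with alpha = 0.5, 6 total measures, 0.3 for correlation between repeated measures" and continue with 192 participants, an effect size of 0.1 and an SD of 5, for a stated power above 90%.

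The Data Analysis text under Statistical Methods says only that the model will "compare the outcome measures of EPDS and GAD-7 between Group 1 (VCI) and Group 2 (AC) at up to six time points".

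The questionnaire schedule puts the first measure before the intervention: "T1 = enrollment; T2 = after group session 9; T3 = 2 months post session 9", then every two months to T6. The section on procedures performed for research purposes gives the same schedule. Aim 1 gives a different one: three time points in pregnancy and then 2, 4 and 6 months postpartum.

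No section names a primary visit, a post-intervention average, adjustment for the enrollment score, or how time is coded. EPDS is called the measure of the primary outcome; GAD-7 shares the Aim 1 hypothesis.

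**The concern.** The hypothesis and the named effect ask different questions. The hypothesis asks whether VCI scores are lower after the sessions. The interaction asks whether the gap between arms differs across the six visits, in any pattern and either direction. A benefit that appears at T2 and holds to T6 enters the interaction only as the step from T1 to T2, and that one step is tested on five degrees of freedom.

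Two things are at stake. First, the stated power belongs to a test that does not by itself answer Aim 1. Second, with five post-intervention visits, two scales and no named contrast, the comparison that carries the Aim 1 claim could be chosen after the data are seen.

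**Working it through.** **Inputs.** From the power paragraph: SD 5, correlation 0.3, m = 6 measures, N = 192, f = 0.1. From the enrollment goals: equal allocation, so 96 per arm. Assumed: alpha 0.05 (0.5 is printed), equal correlation between all visits, complete data, no clustering by session group.

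**Reproducing the plan's figure.** For the two-arm RMANOVA interaction, λ = f²·N·m/(1 − ρ) = 0.01 × 192 × 6/0.7 = 16.46, with (2 − 1)(6 − 1) = 5 and (192 − 2) × 5 = 950 df. Power is 89.8%, essentially the stated figure. At the printed alpha of 0.5 it would be 99.6%. The between-arm main effect at f = 0.1 gives 57%. The stated power therefore fits the 5-df interaction at 0.05.

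**Interaction, for arm gaps d at T1 to T6.** λ = (N/4)·Σ(d − d̄)²/[SD²(1 − ρ)] = 48·Σ(d − d̄)²/17.5. For a gap of 0 at T1 and a steady g at T2–T6, Σ(d − d̄)² = (5/6)g².

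- g = 1: 48 × 0.833/17.5 = 2.29, power 17%
- g = 1.5: 48 × 1.875/17.5 = 5.14, power 37%
- g = 2: 48 × 3.333/17.5 = 9.14, power 63%

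Here f = 0.0373 per point, so f = 0.1 needs 0.1/0.0373 = 2.68 points at every post-intervention visit.

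**Mean of T2–T6 adjusted for T1 (1 df).** Residual variance = 25(1 + 4 × 0.3)/5 − (0.3 × 25)²/25 = 11 − 2.25 = 8.75. SE = √(2 × 8.75/96) = 0.427. Gaps of 1, 1.5 and 2 points are 2.34, 3.51 and 4.68 SEs, giving 64%, 94% and 99.7% (t with 189 df). Simulation with 4,000 replicates agreed at 1.5 points (37% and 94%) and at 2 points.

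**Other shapes, same inputs.**

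| VCI-favouring gap, T2 to T6 | Σ(d − d̄)² | Interaction | Adjusted mean |
|---|---|---|---|
| Growing 0.59 per visit | 6.0 | 90% | 98% |
| Growing 1 per visit | 17.5 | >99.9% | >99.9% |
| 3, 2, 1, 0, 0 | 8.0 | 97% | 80% |
| 2, 1, 0, −1, −2 | 10.0 | 99% | 5% |

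The last row has no average benefit. A steady 2-point harm makes the interaction significant as often as a steady 2-point benefit, 63%.

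**Sensitivity to the correlation.** At 0.5 the interaction's divisor is 25 × 0.5 = 12.5, so λ = 3.20, 7.20 and 12.80 and power is 23%, 51% and 80% for 1, 1.5 and 2 points. The mean contrast does not change, because 25 × 3/5 − 12.5²/25 = 15 − 6.25 = 8.75 again. At 0.7 and 1.5 points the comparison is 77% against 98%.

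**Sensitivity to N.** With all 240 enrolled and correlation 0.3, a steady 1 point gives 21% against 74%, and 1.5 points 46% against 97%.

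**The case against.** The strongest reply is that the plan never makes the interaction the Aim 1 test. It appears only as what the sample is powered for, and the analysis sentences, which compare the arms at the six time points, leave room for visit-wise or averaged differences from the same model. This is correct. A reader might infer that an omnibus interaction has been declared the deciding test, but the documents do not say so. What remains is that nothing else has been declared either.

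A reader might also infer that an early benefit followed by later harm would count as success. The documents do not support that: the hypothesis is directional, and no section says that a significant interaction of any shape confirms it. The 99% figure describes the F test, not a decision rule in the plan.

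Nor is a sustained benefit likely to be missed in general. That holds at 1 and 1.5 points under the plan's inputs, but not at 2 points (63%), 2.5 (85%) or 2.68 (90%). The documents give no minimum important difference that would single out the smaller gaps.

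Finally, the steady gap is one chosen alternative. The power paragraph's gloss of about 1 point per time point reads more naturally as a growing gap, and for that shape the interaction is not weak. The adjusted mean is at least as strong there, though, so the reply does not favour the interaction. A brief benefit does. A single named visit would also close the gap in the plan; the T2–T6 average is preferred because the hypothesis refers to scores across the whole follow-up.

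**Conclusion.** The point holds as a gap in prespecification with a measurable cost. Aim 1 has no named contrast, and the one effect that is named and powered cannot by itself establish that post-intervention scores are lower in VCI. For steady benefits of 1 to 2 points the interaction has 17% to 63% power, against 64% to 99.7% for the adjusted mean. The difference narrows at higher correlation but remains, and the ordering reverses when the benefit fades quickly.

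The figures rest on the assumptions listed in the working. Clustering by session group or missing visits would change the absolute power of both tests. The plan applies the same SD of 5 to both scales, so the figures stand for GAD-7 only as far as that SD does. The change is worth making before unblinded analysis; the planned model itself can stay.

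**What to change.** In both Data Analysis sections, state that Aim 1 is decided by the VCI minus AC difference averaged over T2–T6, adjusted for the T1 score, from the planned mixed model with visit as a categorical factor. Specify it for EPDS, the stated primary outcome, and define the GAD-7 contrast in the same form. Base the stated power on this contrast, with alpha stated correctly. Report the difference with its confidence interval at each visit, and keep Intervention X Time as a secondary test of whether the effect builds or fades.

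Define the contrast on the T1–T6 schedule given with the questionnaires, and reconcile the different schedule under Aim 1 with it.

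The cost is SAP wording, one contrast from a model already planned, and a revised power statement. The T1 score is already collected. The drawback is lower power if the benefit is brief (80% against 97% in the fading example), a case the secondary test still covers.
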